3.2.6 Patient Data Collection

The patient questionnaire will be self-administered (closed-ended questions with predefined answers) on hard copy forms at the site. While there are a number of advantages to using an electronic format for questionnaire administration, we anticipate a paper format will be

preferred in this case based on the study population (e.g., older patients). Written informed consent will be obtained from each patient prior to completion of this questionnaire.

Patients will be asked to complete the questionnaire in the physician's office in a private setting. Sites will provide patients with appropriate privacy so there is no influence by the physician (or patient perception thereof) in this process. Patients will be asked to complete the questionnaire without referring to the patient alert card. Once they have completed the questionnaire, the patient will be asked to review the patient alert card and then re-answer selected questions related to key safety information to gather data on patient knowledge immediately after exposure to the card. Patients will then place their completed forms in an envelope and give the sealed envelope to a study coordinator or designee. While participating physicians will be informed of the purpose of the study, they will be counselled not to alter routine practice and patient education so as not to influence the study results. Physicians will be advised that the ultimate goal of the study is to evaluate the educational materials.

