 **Xarelto**
rivaroxaban

Prescribing Information can be found on pages 10 and 11

211 mm

DO NOT PRINT GUIDES

297 mm

Bayer HealthCare have designed this educational pack to support you in the appropriate prescribing of Xarelto. It contains important information specifically relating to 15mg and 20mg dosing of Xarelto, for use in stroke prevention in AF and treatment of DVT and PE.

Within this pack you will find a:

- Prescriber guide
- Summary of product characteristics (SmPC)
- Patient alert card

If you would like to order more copies of the Xarelto educational pack, please visit www.xarelto-info.co.uk

Alternatively, please contact Bayer Medical Information at [contact] or call [name].

DO NOT PRINT GUIDES

211 mm

**NOW UPDATED
AND INCLUDES A
NEW INDICATION**

XARELTO® (RIVAROXABAN)

PRESCRIBER GUIDE

FOR 15MG AND 20MG DOSING

Prescribing information can be found
on pages 10 and 11

This guide is to be used to support the appropriate use of Xarelto in eligible atrial fibrillation (AF) patients and for the treatment of deep vein thrombosis (DVT) and pulmonary embolism (PE).

It includes the following information:

- **Indications**
- **Dosing recommendations**
- **Populations potentially at higher risk of bleeding**
- **Perioperative management**
- **Overdose**
- **How to manage bleeding complications**
- **Coagulation testing**

Xarelto patient alert card

You must provide a patient alert card to each patient who is prescribed Xarelto 15mg or 20mg.

Please explain the implications of anticoagulant treatment to patients, in particular highlighting the need for:

- treatment compliance
- taking medication with food
- signs or symptoms of bleeding
- when to seek medical attention.

The patient alert card will inform treating physicians and dentists about the patient's anticoagulation treatment and will contain emergency contact information.

Please instruct patients to carry the patient alert card with them at all times and present it to every health care provider.

INDICATIONS

Prevention of stroke and systemic embolism in adult patients with non-valvular AF with one or more risk factors, such as congestive heart failure, hypertension, age \geq 75 years, diabetes mellitus, prior stroke or transient ischaemic attack.

Treatment of DVT and PE and prevention of recurrent DVT and PE in adults. (See section 4.4 of the SmPC for haemodynamically unstable PE patients).

DOSING RECOMMENDATIONS

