Appendix B.
Xarelto Patient Alert Card

What should I know about Xarelto®?

- Xarelto® thins the blood, which prevents you from dangerous blood clots.
- Xarelto® must be taken exactly as prescribed by your doctor. To ensure optimal protection from blood clots, **never skip a dose.**
- You must not stop taking Xarelto® without first talking to your doctor as your risk of blood clots may increase.
- Speak to your health care provider prior to any intake of other medication.
- Inform your health care providers about Xarelto® intake prior to any surgery or invasive procedure.

When should I seek advice from my health care provider?

When taking a blood thinner such as Xarelto® it is important to be aware of its possible side effects. Bleeding is the most common side effect. Do not start taking Xarelto® if you are at risk of abnormal bleeding, without first discussing this with your doctor.

Tell your health care provider right away if you have any signs or symptoms of bleeding such as the following:

- pain
- swelling or discomfort
- headache, dizziness or weakness
- unusual bruising, nosebleeds, bleeding of gums, bleeding from cuts that take a long time to stop

- menstrual flow or vaginal bleeding that is heavier than normal
- pink or brown urine, red or black stools
- coughing up blood, or vomiting blood or material that looks like coffee grounds.

How do I take Xarelto®?

- To ensure optimal protection, Xarelto® 15mg and 20mg must be taken with food.

Date of preparation: November 2012
L.GB.10.2012.0954

PATIENT ALERT CARD

Xarelto® 15mg
Xarelto® 20mg

- **Keep this card with you at all times**
- **Present this card to every physician or dentist prior to treatment**

I am under anticoagulation treatment with Xarelto® (rivaroxaban)

Name: _____

Address: _____

Birth date: _____

Blood type: _____

Weight: _____

Other medications/conditions: _____

In case of emergency, please notify:

Doctor's name: _____

Doctor's phone: _____

Doctor's stamp: _____

Please also notify:

Name: _____

Phone: _____

Relationship: _____

Information for health care providers:

- INR values should not be used as they are not a dependable measure of the anticoagulant activity of Xarelto®.

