- I don't know

Q5. I need to speak to my doctor prior to any intake of other medication(s).

- Yes, this is true
- No, this is not true
- I don't know

Q6. I need to inform my doctor or dentist about Xarelto intake prior to any kind of surgery or invasive procedure.

- Yes, this is true
- No, this is not true
- I don't know

Q7. I need to tell my doctor right away if I have any signs or symptoms of bleeding while taking Xarelto.

- Yes, this is true
- No, this is not true
- I don't know

Q8. Should Xarelto (15 mg and 20 mg tablets) be taken with food?

- Yes
- No
- I don't know

Q9. What should you do to ensure Xarelto is effective in preventing blood clots?

Select all that apply.

- Take Xarelto exactly as prescribed by your Health Care Professional
- Take Xarelto only when you do not feel well
- Do not miss a dose of Xarelto
- I don't know

The next section is about the Xarelto Patient Alert Card that you reviewed before completing the second questionnaire. The Xarelto Patient Alert Card contains important safety information about Xarelto.

Q10. Prior to today, had you received or been given the Patient Alert Card for Xarelto?

- Yes → **Go to Q11**
- No → **Go to Q15**
- I don't remember → **Go to Q15**

Answer questions Q11 – Q14 only if you received a Patient Alert Card for Xarelto.

Q11. Prior to today, had you ever read the Patient Alert Card for Xarelto?

- Yes → **Go to Q13**
- No → **Go to Q12**
- I don't remember → **Go to Q13**

Q12. Is there a reason why you have not read the Patient Alert Card for Xarelto, prior to today?

Select all that apply.

- I haven't taken the medication yet
- Someone else explained it to me
- I lost the patient alert card
- I already knew the information
- I have not had the time yet
- I am not interested in reading it
- Other

Q13. How much of the time do you keep the Xarelto Patient Alert Card with you?

Select the one answer that best applies to you

- All the time
- Some of the time
- None of the time
- I don't know

Q14. Who do you show the Patient Alert Card to?

Select the one answer that best applies to you

- Every doctor or dentist that I visit
- No one, it is just for my information
- Only to healthcare professionals who ask for it
- I don't know

Q15. Prior to today, had someone explained the information in the Patient Alert Card for Xarelto to you?

Select all that apply.

- Yes, a doctor
- Yes, a nurse
- Yes, a pharmacist or someone at the chemists
- Yes, a friend, family member, or carer
- No

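### Patient Questionnaire #2 Q14, the only item on presenting the alert card, has no answer for patients who show it unasked to some but not all of their doctors or dentists

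*Protocol*

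**What the plan says.** The message appears in three places, each with a different description of the audience.

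- Prescriber Guide (Protocol, Appendix A, patient alert card text): "Please instruct patients to carry the patient alert card with them at all times and present it to every health care provider".
- Patient Alert Card (Appendix B): "Present this card to every physician or dentist prior to treatment".
- Patient Questionnaire #2, Q14 (Appendix D): "Who do you show the Patient Alert Card to", with one answer to be selected as the best fit. The options are "Every doctor or dentist that I visit", "No one, it is just for my information", "Only to healthcare professionals who ask for it", and don't know.

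Q14 goes only to patients who already had a card: "Answer questions Q11 – Q14 only if you received a Patient Alert Card for Xarelto". Section 3.2.6 sets the place of completion: "Patients will be asked to complete the questionnaire in the physician's office in a private setting". The third objective in section 2 includes finding out whether patients use and carry the card, and section 3.2.5 lists receipt and use of the card among the concepts assessed.

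**The concern.** A single-choice item should offer every respondent one true answer. Q14 does not. Take a patient who hands the card unprompted to the cardiologist but never to the dentist. The first option is false, because not every provider sees it. The second is false, because someone does. The third is false, because the patient does not wait to be asked. Don't know is also false. No write-in or residual option remains.

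Presenting the card is an obvious form of using it, and no other item asks about it. Incomplete presenting of this kind is one of the shortfalls that an evaluation of the card should be able to show. If the category is not offered, those patients are spread over the other answers in unknown proportions, and the analysis cannot separate them afterwards.

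**Working it through.** **Step 1: is Q14 the only item on presenting?** In the patient forms, Questionnaire #1 Q12 (repeated as Questionnaire #2 Q6) asks about telling a doctor or dentist before surgery, which a patient can do without the card. Questionnaire #2 Q11 asks about reading the card, Q13 about carrying it and Q15 about having had it explained. In the physician questionnaire (Appendix C), Q21 to Q23 cover receiving, distributing and discussing the card. None asks whether patients show it, so Q14 is the only measure.

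**Step 2: how do neighbouring items treat partial behaviour?**

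| Item | Behaviour | Intermediate level | Residual option |
|---|---|---|---|
| Questionnaire #2 Q13 | Carrying the card | Yes (some of the time) | No |
| Physician Q22 | Giving out cards | Yes (most, a few) | No |
| Questionnaire #1 Q6, Q16; Questionnaire #2 Q12 | Information source, indication, reason for not reading | Not applicable | Yes (other) |
| Questionnaire #2 Q14 | Presenting the card | Only presenting on request | No |

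Q14 has an intermediate answer for presenting on request, but none for presenting unasked to some providers.

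**Step 3: who has had no occasion to present?** Questionnaire #1 Q2 allows for use of less than 1 month, so very recent recipients can be included. Against that, Q14 respondents had the card before the day of completion and fill in the form at the physician's office, so most are at a provider contact when they answer. The remaining group is recent recipients who have made no other visit, and it is likely to be small.

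**Step 4: provider wording.** The guide covers every health care provider, the card covers physicians and dentists, and Q14's first option covers doctors and dentists. A patient can truthfully tick that option without ever showing the card to a nurse or pharmacist. Q14's third option uses the wider term, health care professionals, so the item mixes two scopes.

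**Step 5: the plan's precision.** With half-width = 1.96 × √(p(1 − p) × DE / n), p = 0.5 and n = 500:

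- DE = 1: 1.96 × √(0.25/500) = 4.4 points, giving 45.6% to 54.4%, as in section 3.2.4.
- DE = 4 (intraclass correlation 0.33): 8.8 points, giving 41.2% to 58.8%, as stated there.

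These are best cases for Q14, because only prior card recipients answer it and the 18-month assessment targets 400 patients. If 60% of 500 had a card (an assumption), n = 300 and the half-width without clustering is 1.96 × √(0.25/300) = 5.7 points.

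**Step 6: possible effect on the first option.** Let f be the share of recipients with no fitting option and g the share of those who tick the first option. The overstatement is f × g. The protocol gives neither value, so these are assumed ranges, in percentage points:

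| f | g = 0 | g = 0.5 | g = 1 |
|---|---|---|---|
| 5% | 0 | 2.5 | 5 |
| 10% | 0 | 5 | 10 |
| 20% | 0 | 10 | 20 |

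The effect runs from nothing to more than the sampling error. The documents do not indicate which cell applies.

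**The case against.** A reader might infer that full presenting itself is mis-measured, or inflated by tens of points. The documents do not support that. Full presenting has its own option, worded much like the card's instruction. Its share is biased upwards only if misfitting patients tick it. On a paper form they could equally tick the on-request option or don't know, or leave the item blank. Any large inflation figure comes from assumed shares that have no anchor in the protocol.

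Nor is failure to present lost altogether: the no-one and on-request options capture two forms of it, and only one intermediate group is missing. The no-occasion case is weakened by completion at the physician's office, by a stem that asks about habit, and by the don't-know option.

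The consequence is also limited. Presenting to every provider is not among the key safety messages listed in section 1 or section 3.2.5. Carrying the card and informing professionals before surgery are on those lists, and both are measured. Q14 is one descriptive item, with no threshold or test attached to it in the protocol.

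All of this stands and keeps the point minor. It does not make the options exhaustive. Cognitive pretesting with 25 patients (section 3.3) does not supply the missing category either.

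**Conclusion.** The point holds as a minor defect in Appendix D, Questionnaire #2 Q14. The guide and the card are the messages being measured, and the error is not in them. Partial presenting without being asked cannot be recorded, so those patients are misclassified. This follows from the option list alone and needs no assumption.

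The size and direction of any bias in the first option's share are undetermined. Under the assumed ranges above it is 0 to 20 points, and zero is possible. The no-occasion gap is real but narrow. The different provider terms in guide, card and Q14 are a separate small inconsistency that affects what the first option means.

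**What to change.** Before fielding:

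1. Add to Q14 an option such as *Some of the doctors or dentists I visit, without being asked*.
2. Add a no-occasion option such as *I have not visited a doctor or dentist since I received the card*, and report full presenting among recipients with at least one visit.
3. Reconcile the description of the audience across the Prescriber Guide, the Patient Alert Card and Q14, so that the first option measures the message the patient was given.

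The cost is a small edit and re-translation of a pretested paper form, and a slightly smaller base for one descriptive item. Section 1 plans assessments at 18 months, 3 years and 7 years. Making the change before the first keeps Q14 comparable across all three. A later change would alter the option set between waves.

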Appendix B.
Xarelto Patient Alert Card

What should I know about Xarelto®?

- Xarelto® thins the blood, which prevents you from dangerous blood clots.
- Xarelto® must be taken exactly as prescribed by your doctor. To ensure optimal protection from blood clots, **never skip a dose.**
- You must not stop taking Xarelto® without first talking to your doctor as your risk of blood clots may increase.
- Speak to your health care provider prior to any intake of other medication.
- Inform your health care providers about Xarelto® intake prior to any surgery or invasive procedure.

When should I seek advice from my health care provider?

When taking a blood thinner such as Xarelto® it is important to be aware of its possible side effects. Bleeding is the most common side effect. Do not start taking Xarelto® if you are at risk of abnormal bleeding, without first discussing this with your doctor.

Tell your health care provider right away if you have any signs or symptoms of bleeding such as the following:

- pain
- swelling or discomfort
- headache, dizziness or weakness
- unusual bruising, nosebleeds, bleeding of gums, bleeding from cuts that take a long time to stop

- menstrual flow or vaginal bleeding that is heavier than normal
- pink or brown urine, red or black stools
- coughing up blood, or vomiting blood or material that looks like coffee grounds.

How do I take Xarelto®?

- To ensure optimal protection, Xarelto® 15mg and 20mg must be taken with food.

Date of preparation: November 2012
L.GB.10.2012.0954

PATIENT ALERT CARD

Xarelto® 15mg
Xarelto® 20mg

- **Keep this card with you at all times**
- **Present this card to every physician or dentist prior to treatment**

I am under anticoagulation treatment with Xarelto® (rivaroxaban)

Name: _____

Address: _____

Birth date: _____

Blood type: _____

Weight: _____

Other medications/conditions: _____

In case of emergency, please notify:

Doctor's name: _____

Doctor's phone: _____

Doctor's stamp: _____

Please also notify:

Name: _____

Phone: _____

Relationship: _____

Information for health care providers:

- INR values should not be used as they are not a dependable measure of the anticoagulant activity of Xarelto®.

Appendix C.

Physician Questionnaire

To confirm your eligibility to participate in this brief assessment, please answer the following question:

S1. In the past 6 months, have you prescribed Xarelto (rivaroxaban) to patients for either of the following indications?

(Tick all that apply.)

- Prevention of stroke and systemic embolism in adult patients with non-valvular atrial fibrillation
- Deep vein thrombosis treatment and secondary prevention in adults
- I have not prescribed Xarelto for either of these indications

[IF S1 = “I have not prescribed Xarelto for either of these indications”, THEN DISPLAY “It does not appear that you qualify for the survey. Thank you for your time and interest.” AND TERMINATE SURVEY ELSE DISPLAY “We have confirmed that you are eligible. We will now continue with the survey questions].

Physician Questionnaire

This questionnaire is designed to gain a better understanding of prescribers’ knowledge about Xarelto for only the following two approved indications:

- Prevention of stroke and systemic embolism in adult patients with non-valvular atrial fibrillation
- Deep vein thrombosis treatment and secondary prevention

Additionally, this assessment will be used to determine if the education materials regarding Xarelto, including the Prescriber Guide, are accurately understood and whether there are aspects of these materials that could be improved.

The first set of questions asks about your prescribing practices.

Q1. In the past 6 months, for how many patients have you prescribed Xarelto for the prevention of stroke and systemic embolism in patients with non-valvular atrial fibrillation?

- 1 to 10
- 11 to 20
- 21 or more
- I have not prescribed Xarelto for this indication

Q2. In the past 6 months, for how many patients have you prescribed Xarelto for deep vein thrombosis treatment and secondary prevention?

- 1 to 10
- 11 to 20
- 21 or more
- I have not prescribed Xarelto for this indication

Q3. When did you write your most recent prescription for Xarelto for either of these indications?

(Tick one.)

- Less than 1 month ago
- 1 to 3 months ago
- 4 to 6 months ago
- I don't know

Q4. Which of the following Xarelto treatment activities are you responsible for?

(Tick all that apply.)

- I initiate Xarelto treatment or convert treatment from or to Xarelto
- I write follow up (maintenance) prescriptions for Xarelto

The next questions ask about the use of Xarelto for prevention of stroke and systemic embolism in patients with non-valvular atrial fibrillation and deep vein thrombosis treatment and secondary prevention.

Q5. What is the most important risk associated with taking Xarelto?

(Tick one.)

- Neoplasia
- Hypertension
- Risk of bleeding
- Immunosuppression
- I don't know

Q6. Which of the following populations are at an increased risk of experiencing serious side effect(s) associated with Xarelto?

(Tick Yes, No, or I don't know for each patient population listed)

| Population | Yes, at higher risk | No, not at higher risk | I don't know |
|--|--------------------------|---------------------------|--------------------------|
| Patients with moderate or severe renal |  |  |  |

| | | | |
|---|--------------------------|--------------------------|--------------------------|
| impairment | | | |
| Patients taking products that affect hemostasis such as NSAIDS, acetylsalicylic acid, platelet aggregation inhibitors |  |  |  |
| Patients at risk of bleeding |  |  |  |
| Patients with chronic constipation |  |  |  |

Q7. To which patient groups is Xarelto contraindicated?**(Tick all that apply.)**

- Patients with hepatic disease associated with coagulopathy and clinically relevant bleeding risk including cirrhotic patients with Child Pugh class B and C
- Patients who are pregnant or breastfeeding
- Patients receiving concomitant treatment with any other anticoagulant such as unfractionated heparin (UFH), low molecular weight heparins, heparin derivatives or oral anticoagulants except when switching therapy to or from Xarelto or when UFH is given at doses necessary to maintain a patent central venous or arterial catheter
- Patients with clinically significant active bleeding
- I don't know

Q8. Xarelto (15 or 20 mg) must be taken....?**(Tick one.)**

- On an empty stomach
- With food/on a full stomach
- I don't know

Q9. Is routine coagulation monitoring required for patients taking Xarelto for these indications?

- Yes
- No
- I don't know

Q10. In which of the following situations is INR monitoring needed?**(Tick all that apply.)**

- When converting from vitamin K antagonist (VKA) (e.g., warfarin) to Xarelto
- When converting from Xarelto to VKA
- Continual INR monitoring is required for all patients taking Xarelto
- I don't know

Q11. Which of the following steps should be taken when converting patients from VKA (e.g., warfarin) to Xarelto?

(Tick all that apply.)

- Stop VKA without measuring INR
- For patients treated for prevention of stroke and systemic embolism, stop VKA and initiate Xarelto when INR is ≤ 3
- For patients treated for deep vein thrombosis and secondary prevention, stop VKA and initiate Xarelto when INR is ≤ 2.5
- I don't know

Q12. Which of the following steps should be taken when converting patients from Xarelto to VKA (e.g., warfarin)?

(Tick all that apply.)

- Overlap the two drugs until INR is ≥ 2.0
- Measure INR but make sure it has been longer than 24 hours since the last dose of Xarelto
- Stop Xarelto at any time
- Measure INR at any time of the day
- I don't know

Q13. Which of the following are true when converting from parenteral anticoagulants to Xarelto...?

(Tick all that apply.)

- Stop parenteral anticoagulants for a week prior to starting Xarelto
- For patients with continuously administered parenteral anticoagulants such as intravenous unfractionated heparin, Xarelto should be started at time of drug discontinuation
- For patients with parenteral drug on a fixed dosing scheme such as low molecular weight heparin (LMWH), Xarelto should be started 0 to 2 hours before the next scheduled drug administration
- I don't know

Q14. If an invasive procedure or surgical intervention is required, when should treatment with Xarelto (15 to 20 mg) be suspended (if possible, based upon clinical judgement of physician)?

(Tick one.)

- One week prior to the procedure or surgical intervention
- At least 24 hours prior to the procedure or surgical intervention
- It is not necessary to stop Xarelto for these procedures
- I don't know

Q15. What are the most appropriate actions you should take if a patient taking Xarelto presents with a medically important bleeding complication?

(Tick all that apply.)

- Provide symptomatic treatment (e.g., mechanical compression, surgery)
- Delay the next administration of Xarelto or discontinue Xarelto as appropriate
- Provide hemodynamic support (e.g., blood transfusion)
- Administer procoagulant reversal agent (for life-threatening bleeding)
- Refer the patient to emergency care
- None of the above
- I don't know

[IF Q1 = "I have not prescribed Xarelto for this indication", SKIP TO intro text preceding Q18.]

The following questions are about the indication for prevention of stroke and systemic embolism in patients with non-valvular atrial fibrillation.

Q16. What is the standard recommended dose of Xarelto for the prevention of stroke and systemic embolism in patients with non-valvular atrial fibrillation?

(Tick one.)

- 20 mg taken once a day
- 15 mg taken once a day
- 10 mg taken once a day
- None of the above
- I don't know

Q17. What is the recommended dose for patients with moderate or severe renal impairment (creatinine clearance of 15-49 mL/min) receiving Xarelto for the prevention of stroke and systemic embolism in patients with non-valvular atrial fibrillation?

(Tick one.)

- 20 mg taken once a day
- 15 mg taken once a day
- 10 mg taken once a day
- None of the above
- I don't know

[IF Q2 = "I have not prescribed Xarelto for this indication", SKIP TO intro text preceding Q19.]

The following questions are about the indication for deep vein thrombosis treatment and secondary prevention in adult patients.

Q18. What is the standard recommended dose for patients receiving Xarelto for deep vein thrombosis treatment and secondary prevention?

(Tick one.)

- 20 mg twice a day for the first three weeks of administration, followed by 20 mg taken once a day
- 15 mg twice a day for the first three weeks of administration, followed by 20 mg taken once a day
- 10 mg once a day
- None of the above
- I don't know

In this next section, please tell us about any information you have received about Xarelto.

Q19. From which of the following sources did you receive information about Xarelto?

(Tick all that apply.)

- Xarelto Prescriber Guide
- Briefing from a company representative
- Discussion with a clinical expert
- The Summary of Product Characteristics for Xarelto
- Clinical trials published in the medical literature
- Other
- None of the above

Q20. How helpful were these sources to you in treating and educating your patients?

[ONLY DISPLAY RESPONSES THAT WERE CHECKED IN Q19; IF Q19 = “NONE OF THE ABOVE”, SKIP TO Q21.]

| | 1 Not at all helpful | 2 | 3 | 4 | 5 Extremely helpful |
|--|-------------------------------------|--------------------------|--------------------------|--------------------------|------------------------------------|
| Xarelto Prescriber Guide |  |  |  |  |  |
| Briefing from a company representative |  |  |  |  |  |
| Discussion with a clinical expert |  |  |  |  |  |
| Summary of Product Characteristics |  |  |  |  |  |
| Medical Publications |  |  |  |  |  |
| Other |  |  |  |  |  |

Q21. Have you received Xarelto Patient Alert Cards to provide to your patients?

- Yes
- No

[IF Q21 IS NO, SKIP TO Q23.]

Q22. Considering the Xarelto patients under your care, to how many did you provide a Patient Alert Card?

- Every one of my patients
- Most of my patients
- A few of my patients
- None of my patients

Q23. When would you discuss the information on the Patient Alert Card with your patients taking Xarelto?

(Tick all that apply.)

- When first prescribing Xarelto
- When a patient is facing an invasive procedure or surgical intervention
- When a patient has bleeding complications
- When a patient has a Xarelto related adverse event
- I do not use the Patient Alert Card
- Other

In this next section, please tell us a little about yourself and your clinical practice.

Q24. Which of the following best describes your specialty?

- General medicine
- Neurology
- Cardiology
- Haematology
- Accident & Emergency medicine
- Oncology
- Other

Q25. How many years have you been practicing medicine?

- 5 years or less
- 6 to 10 years
- 11 to 15 years
- 16 to 20 years
- 21 to 25 years
- More than 25 years

Q26. Are you...?

- Male
- Female

Q27. How would you characterise your practice?

(Tick all that apply.)

- General practice
- Hospital-based clinic
- Nursing home
- Other

0302949 Physician Questionnaire

Thank you for completing the questionnaire!

In order to continue to monitor and evaluate the safety of Bayer products, the sponsor is interested in any adverse events that have not already been reported. If you have any such adverse events to report for your patients, please do so using the contact information provided here.

[Contact information will be inserted in the survey or on the contact page.]

If you would like additional information or have any questions about the prescribing guidelines or safety information related to Xarelto, please click to the link below to access the Xarelto Prescriber Guide.

[INSERT LINK]

